Risk of Injury and Discomfort: The side effects of tACS are mild and transient; in fact, low intensity transcranial current stimulation, such as tACS, has been used for several years without any report of serious side effects [10]. Furthermore, this stimulation mode has nothing to do with electroconvulsive therapy that applies many orders of magnitude higher stimulation current. Rather, transcranial current stimulation is so weak that it does not cause super-threshold activation of neurons [11]. However, tACS does have some mild side effects, such as transient mild tingling, burning, or itching under the electrode sites. In our previous trial, subjects from all three groups of stimulation reported either absent or mild side effects, and there was no difference between the groups with the exception of “flickering lights” (or phosphenes, $p = 0.014$)[6]. To monitor these mild side effects, we will be administering a stimulation questionnaire after each stimulation session to determine whether these effects were experienced and at what intensity. Research personnel is present during the full experimental. If subject is experiencing severe discomfort (as determined by the questionnaire or by self-report), the stimulation will be stopped immediately.

Patients with MDD have an about 20 times higher rate of suicide than average. We have no evidence that our treatment paradigms will in any way increase this likelihood. In the previous iteration of this trial, 4 subjects in the sham/placebo stimulation group experienced an increase in suicidal thoughts and only one of those 4 subjects reported suicidal intent [6]. No subjects who received tACS reported an increase in suicidal ideation from baseline. Regardless, subjects with high suicide risk will not be included in this study. If an enrolled subject shows signs of suicide risks that were not apparent during enrollment, a referral to UNC Psychiatry will be made. [name], Co-I, will facilitate this process.

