9.2 SAMPLE SIZE DETERMINATION

In our recently concluded pilot clinical trial we compared the effects of 10 Hz tACS (therapeutic frequency) against 40 Hz tACS (control frequency) and sham/placebo stimulation. A total of 32 subjects enrolled, 30 completed the 5-day intervention, and 26 completed both a 2 and a 4-week follow-up session. With approximately 9 subjects in each group, a significant reduction was found in alpha oscillation power on the fifth day of stimulation ($p < 0.05$) [6]. Therefore, with a total of 20 subjects (10 in each group), we anticipate we will find a significant difference. Of note, our funding mechanism covers the cost of enrolling 20 participants.

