9.4 STATISTICAL ANALYSES

9.4.1 GENERAL APPROACH

All testing described below assumes a significance threshold of $p = 0.05$. Continuous data will be described using means and standard deviations, while categorical data will be described using counts/percentages.

There will be no pre-specified covariates described in this protocol. Data will be assessed for normality and, if deemed necessary, corrective procedures will be applied (e.g., log normalization).

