9.4.4 SAFETY ANALYSES

As discussed in **Section 8.2, Safety and Other Assessments** safety will be assessed with the three questions from the daily suicide questionnaire, the C-SSRS, an adverse effects questionnaire, and the Young Mania Rating Scale (YMRS).

The suicide questionnaire is used as a screening to assess increase in suicidal ideation (SI) or suicidal behavior (SB) daily. The C-SSRS will be used to assess suicide risk more thoroughly. If a participant's responses on either tool indicate SI or SB, the subject will be contacted, and an acute assessment will be completed if deemed necessary by [name] or [name] (as described above). Any verified increases in suicidal ideation will be described in counts/percentages and compared between groups using chi-square tests.

The stimulation questionnaire will be administered following every stimulation session, for a total of 5 administrations per participant. This questionnaire solicits ratings of 14 possible adverse effects associated with electrical stimulation, on a scale of 1 (absent) to 4 (severe). Paired t-tests with random effect "subject" will be calculated per adverse effect to determine if there are any differences in adverse effect severity between groups (sham/placebo, 10 Hz tACS). Severity per adverse effect will be described with mean and standard deviation.

The Young Mania Rating Scale (YMRS) will be used to assess any development of mania over the course of treatment. A YMRS score of greater than 12 indicates the possible development of a manic episode. Any subject who scores greater than 12 on the YMRS will be assessed by [name] or [name]. Any verified manic episode will be described in counts/percentages and compared between groups using a chi-square test.

The Adverse Events Structured Interview will be administered by research personnel following every stimulation session and at the follow up visit, for a total of 6 time points per participant. This interview solicits open-ended descriptions of 11 possible adverse effects a participant may experience in any clinical trial as well as one question of 'any other experiences'. Responses will be reviewed by the clinician and rated as described in **Section 8.3**. Paired t-tests will be calculated per adverse effect to determine if there are any differences in adverse effect severity between groups (sham/placebo, 10 Hz tACS). Severity per adverse effect will be described with mean and standard deviation.3.

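### No count of participants by severity grade is planned for the stimulation side-effect ratings; mean and SD alone can place isolated severe reactions near 'absent'

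*Combined protocol and SAP*

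**What the plan says.** Section 9.4.4 describes the stimulation questionnaire as collecting "ratings of 14 possible adverse effects associated with electrical stimulation, on a scale of 1 (absent) to 4 (severe". It is given after every session, "for a total of 5 administrations per participant". For each effect the plan names a t-test between groups and one descriptive summary: "Severity per adverse effect will be described with mean and standard deviation". The section names no count or percentage by grade, no worst grade per participant and no count of severe ratings. It also does not say whether the mean is taken over all five sessions or session by session. Severity from the adverse event structured interview, which a clinician grades under section 8.3, is to be summarised in the same way.

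Other parts of the plan treat comparable data by category. Section 9.4.1 states that "categorical data will be described using counts/percentages". Section 9.4.4 itself uses counts and percentages for verified increases in suicidal ideation and for manic episodes. Section 2.3.1 reports tolerability in the previous trial by grade: "subjects from all three groups of stimulation reported either absent or mild side effects". The same section makes severe discomfort, identified from the questionnaire or by self-report, a reason to stop stimulation.

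**The concern.** The ratings form a four-level ordinal scale on which most values are likely to be 1. For such data a mean mixes how many people had an effect, how bad it was and how often it occurred. A useful tolerability statement says how many participants reached a moderate or severe grade. Section 2.3.1 speaks in those terms about the previous trial, yet the planned summary would not let the authors confirm or contradict a statement of that kind for this one. The protocol acts on the severe category during conduct but plans no report of how many people reached it. At stake is the readability of the tolerability result, not the primary EEG analysis.

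**Working it through.** **Inputs from the documents.** Section 9.2 plans the trial "with a total of 20 subjects (10 in each group"; section 9.4.4 gives five ratings per participant per effect on the 1 to 4 scale. So each effect has 10 × 5 = 50 ratings per arm. The plan states no expected tolerability rate or mean, so there is no planned figure to reproduce.

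**Assumptions, not in the documents.** In the tACS arm, k participants rate an effect 4 in s sessions each, and every other rating is 1. The sham arm is all 1. Ratings are pooled over sessions unless stated otherwise.

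**Step 1: pooled mean and SD.** Mean = 1 + 3ks/50. With m = ks severe ratings, SD² = 9m(1 − m/50)/49. For k = 3, s = 1: mean = 1 + 9/50 = 1.18; SD² = 9 × 3 × 0.94/49 = 0.518, so SD = 0.72.

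| Participants severe once each (of 10) | Pooled mean | SD of 50 ratings |
|---|---|---|
| 2 | 1.12 | 0.59 |
| 3 | 1.18 | 0.72 |
| 4 | 1.24 | 0.82 |

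**Step 2: can the number of reactors be recovered?**
- Nine participants with one mild rating each and nobody severe also give 1 + 9/50 = 1.18. Here SD² = 9 × 0.82/49 = 0.151, so SD = 0.39. The mean does not separate this from three severe reactors; the SD does, without giving a headcount.
- One participant severe in three sessions (k = 1, s = 3) has the same m = 3, hence the same mean of 1.18 and the same SD of 0.72 as three participants severe once each. On pooled ratings, 1/10 and 3/10 look identical. If the SD were instead taken over participant means, the two cases would differ (0.57 against 0.29), but the plan does not say which SD is meant.

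**Step 3: how far the result depends on the pattern.** If the same 2, 3 or 4 participants are severe in all five sessions, the pooled means are 1.60, 1.90 and 2.20. If means are given per session and three severe ratings fall in one session, that session's mean is 1 + 3 × 3/10 = 1.90 (SD 1.45). If they fall in three different sessions, each of those sessions has a mean of 1 + 3 × 1/10 = 1.30. The near-1 result therefore belongs to isolated severe ratings.

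**Step 4: what a count would show.** Three of 10 participants with a worst grade of severe is 30%, exact (Clopper-Pearson) 95% interval 6.7% to 65.2%. Zero of 10 in sham is 0% to 30.8%.

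**Step 5: would counts detect more?** Take an unpaired two-sided t-test on participant means against the all-absent sham arm, at the 0.05 threshold of section 9.4.1. For k = 3, s = 1, the tACS participant means are 1.6 (three people) and 1.0 (seven), with mean 1.18 and SD² = 0.36 × 3 × 0.7/9 = 0.084. Then t = 0.18/√(0.084/10) = 1.96 on 18 degrees of freedom, p = 0.065. For k = 2 and k = 4, p = 0.15 and 0.025. Fisher's exact test on the counts gives p = 0.47, 0.21 and 0.087 for k = 2, 3 and 4. The count is the less sensitive test in every case.

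**The case against.** A fair defence has five parts.

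1. **Pooling is not stated.** Section 9.4.4 does not say the five sessions are averaged, and a random effect for subject suggests session-level ratings. This stands: the 1.12 to 1.24 range is conditional on pooling and on isolated reactions.
2. **The SD is reported too.** This stands in part. The SD separates the mild from the severe pattern above (0.39 against 0.72), but on pooled ratings it cannot separate one participant severe three times from three severe once.
3. **Severe events have other routes.** Section 8.2.3 plans a structured interview after each stimulation day, section 8.3.3.1 grades each event, section 8.3.4 records every event on a case report form, and section 10.1.6 has the principal investigator review them. A reader might infer that severe reactions drop out of the tolerability result. The documents do not support that, because the events remain individually graded and on record. What is missing is a planned tabulation by grade, since the interview severity is also reduced to mean and SD.
4. **Counts are not a stronger test.** This stands. A reader might take p = 0.065 as showing that the planned test misses something a count would find; Fisher's p = 0.21 on the same data shows the opposite. The 0.065 also comes from an unpaired test, whereas 9.4.4 names a paired one. That wording is a separate issue.
5. **Mean and SD are not declared exclusive.** Section 9.4.1 keeps counts for categorical data and could be read to cover these ratings. However, 9.4.4 specifies a continuous summary for them while naming counts for the suicidality and mania outcomes beside them, so an analyst following the text would not produce the table.

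**Conclusion.** The point holds in a limited form. Section 9.4.4 plans mean and SD for a four-level ordinal rating and no count of participants by grade. If ratings are pooled over sessions and severe reactions are isolated, 2 to 4 severe reactors out of 10 give an arm mean of 1.12 to 1.24, and the number of reactors cannot be recovered from that summary. These patterns are illustrations; the documents give no expected rates, and section 2.3.1 reports only absent or mild effects in the previous trial. It would go too far to say that severe reactions always average out: persistent ones give 1.60 to 2.20.

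The analysis set also matters. Section 9.3 builds all analyses on participants who complete five sessions, and section 7.2 replaces those who receive only part of the intervention and then leave. Someone who stops after a severe reaction might therefore be missing from any tolerability table. The documents do not say outright that such people are excluded from the safety analyses, so this is a gap to close, not an established loss. Overall this is a cheap improvement to safety reporting and does not affect the primary EEG result.

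**What to change.** Add to section 9.4.4, for each of the 14 effects:

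- Take each participant's worst rating over all sessions received, and tabulate n (%) by arm at absent, mild, moderate and severe.
- Report the number and percentage rated 3 or 4, with an exact 95% confidence interval.
- Include every participant who received any stimulation, including those who stop early and are replaced. Denominators may then exceed 10 per arm.
- Keep mean and SD as supplementary, and state whether they are per session or pooled and what the SD is taken over.

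The same layout can serve the interview severity grades. The data are already collected, so the cost is a wording change and one extra table. The downside is that intervals will be wide at 10 per arm, and the table should be presented as description and not as a test.

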8.3.3 CLASSIFICATION OF AN ADVERSE EVENT

8.3.3.1 SEVERITY OF EVENT

All adverse events (AEs) will be assessed by the principal investigator and/or co-investigator(s) using the following guidelines:

- **Mild** – Events require minimal or no treatment and do not interfere with the participant's daily activities.
- **Moderate** – Events result in a low level of inconvenience or concern with the therapeutic measures. Moderate events may cause some interference with functioning.
- **Severe** – Events interrupt a participant's usual daily activity and may require systemic drug therapy or other treatment. Severe events are usually potentially life-threatening or incapacitating. Of note, the term "severe" does not necessarily equate to "serious".

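### The structured adverse-event interview is compared between arms only on severity, with no score defined for no event and no planned comparison of the number of participants affected.

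*Combined protocol and SAP*

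**What the plan says.** Section 9.4.4 (Safety Analyses) describes an Adverse Events Structured Interview held after each stimulation session and at follow-up, 6 time points per participant. It asks open-ended questions about 11 named effects and has one catch-all question about other experiences. On scoring it says: "Responses will be reviewed by the clinician and rated as described in" Section 8.3. On analysis it says: "Paired t-tests will be calculated per adverse effect to determine if there are any differences in adverse effect severity between groups". The summary is: "Severity per adverse effect will be described with mean and standard deviation".

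The severity scale in Section 8.3 is in 8.3.3.1 and has three levels. The lowest, mild, is defined by "Events require minimal or no treatment and do not interfere with the participant's daily activities". The middle level, moderate, is for an event that causes limited inconvenience or worry and perhaps some loss of function. The highest, severe, is defined by "Events interrupt a participant's usual daily activity and may require systemic drug therapy or other treatment".

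Elsewhere in 9.4.4, a separate 14-item stimulation questionnaire is scored "on a scale of 1 (absent) to 4 (severe", so an absent effect has a score there. For verified increases in suicidal ideation and for verified manic episodes, 9.4.4 plans counts and percentages with a chi-square test between groups. It plans neither for the interview effects.

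**The concern.** All three levels in 8.3.3.1 describe something that has happened. A participant who reports no headache at any interview has no place on the scale. Taken literally, that participant contributes nothing to the headache mean, and each arm's mean is taken over those who had the event. That subset is formed after randomisation, and its membership may itself depend on treatment.

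Such a comparison asks how bad the event was among those who had it. The first question in a sham-controlled safety comparison is how many people had it in each arm, and the plan sets no between-arm comparison that answers it for these effects. A side effect that active stimulation made more common, but that stayed mild, could be reported as showing no difference.

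If the analyst instead codes unaffected people as zero, the result can change completely. Because the plan does not fix that choice, it could be made after the data are seen.

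**Working it through.** **Inputs from the documents.** 10 per arm (9.2); significance threshold 0.05 (9.4.1), taken as two-sided because sidedness is not stated; three severity levels, none for absence (8.3.3.1); 5 sessions + 1 follow-up = 6 interviews (9.4.4). The plan gives no expected incidence, severity distribution or power for this comparison, so it has no figure of its own to reproduce.

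**Is a zero level defined anywhere?** No. The Not Related category in 8.3.3.2 grades causality, not absence of an event. Section 9.4.1 says that categorical data will be described by counts and percentages, but that is descriptive, and 9.4.4 summarises interview severity by mean and SD.

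**Worked example.** Suppose 8/10 are affected on tACS and 2/10 on sham, half mild (1) and half moderate (2) in each arm. Tests for two independent arms are used, because the arms contain no pairs.

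1. Severity among those affected. tACS: (4×1 + 4×2)/8 = 1.5. Sham: (1 + 2)/2 = 1.5. Difference 0, t = 0 on 8 df, p = 1.00.
2. Severity with no event = 0, over all 10. tACS: 12/10 = 1.2. Sham: 3/10 = 0.3. Sums of squares: 20 − 10×1.2² = 5.6 and 5 − 10×0.3² = 4.1. Pooled variance (5.6 + 4.1)/18 = 0.539. SE = √(0.539 × 2/10) = 0.328. t = 0.9/0.328 = 2.74 on 18 df, p = 0.013.
3. Number affected. Risk difference 0.8 − 0.2 = 0.6. Fisher's exact test: 2 × (45×45 + 10×10 + 1)/184,756 = 2 × 2,126/184,756 = 0.023.

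The same 20 people give p = 1.00 or p = 0.013 according to a scoring choice that the plan leaves open.

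**How often this would matter.** Simulation, 6,000 trials per scenario in the main runs, 10 per arm, one score per person, independent-samples t-test, same severity mix in both arms. Incidences and mixes are assumptions. Where a range is shown, repeat runs differed by simulation error. Severity mixes are mild/moderate/severe.

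| Affected, tACS v sham | Severity mix (%) | Events-only t-test significant | Events-only test not computable | Fisher on numbers affected | t-test with no event = 0 |
|---|---|---|---|---|---|
| 80% v 20% | 60/30/10 | 2.7% | 38% | 63% | 69% |
| 80% v 20% | 80/20/0 | 2.3% to 2.5% | 44% | 63% to 64% | 74% to 75% |
| 70% v 10% | 80/20/0 | 0.8% to 1.0% | 76% to 78% | 66% to 68% | 79% to 80% |
| 70% v 30% | 60/30/10 | 3.7% | 15% | 24% | 35% |
| 60% v 20% | 60/30/10 | 2.5% | 40% | 25% | 40% |
| 40% v 20% | 80/20/0 | not run | not run | 6% | 14% |

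The events-only test never exceeds its nominal 5%, as expected when severity among those affected is the same in both arms. It carries no information about incidence. The last three rows show that comparing numbers affected also has little power against moderate differences at this sample size.

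**The case against.** A reader might infer that the plan excludes unaffected participants, or that its comparison is bound to miss a difference in incidence. The documents do not support that. Every participant is to be interviewed, so a negative answer is recorded data, and coding it zero would be an ordinary choice. What can be said is that the score for no event is undefined. This part of the objection stands and limits the claim.

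A reader might also infer that the test would often be impossible to compute, or would point the wrong way. Those rates are not properties of the plan. They depend on one score per person, whereas the plan has 6 interviews and no rule for combining them (up to 6 × 10 = 60 ratings per arm if pooled), and on an independent t-test where the plan says paired. A reversed mean is possible: with 6/10 affected, all mild, against 1/10, moderate, the events-only means are 1.0 v 2.0, and the zero-scored means are 0.6 v 0.2. But that reversal rests on one person's rating, the events-only test cannot be computed, and the alternatives are not significant either (Fisher p = 0.057; zero-scored p = 0.14). It shows a misleading description, not a wrong test result.

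The gap is also narrower than safety reporting as a whole. Effects linked to electrical stimulation are covered by the 14-item questionnaire, which has an absent level. All adverse events go on case report forms (8.3.4), so counts can be recovered. Section 2.3.1 reports that side effects in the previous trial were absent or mild, with no group difference except phosphenes. These points reduce the stakes but do not close the gap: the interview covers effects possible in any trial, and under 9.4.4 it is repeated at follow-up while the stimulation questionnaire is not. Recoverable counts are also not a planned comparison.

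**Conclusion.** The point holds in a limited form. For the interview effects, 9.4.4 plans a between-arm comparison of severity only, on a scale without a no-event score, and no between-arm comparison of the number affected. If unaffected participants get no value, the comparison is confined to a post-randomisation subset and cannot show a difference in incidence. In the 8/10 v 2/10 example that means p = 1.00 instead of 0.023 or 0.013. Under the assumptions stated, the events-only test is significant in about 1% to 3% of trials with very large incidence differences (80% v 20%, 70% v 10%), where Fisher detects about 63% to 68%.

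The gain should not be oversold. With 10 per arm Fisher detects 25% at 60% v 20% and 6% at 40% v 20%. The main benefit is an estimate with a clear meaning and an interval, together with removal of an analyst's choice that can be made after unblinding. The stimulation questionnaire and the primary EEG analysis are not affected. The change is worth making because it is cheap. The paired wording in the same sentence is a separate fault, and correcting it alone would not resolve this one.

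**What to change.** In 9.4.4, for each of the 11 named interview effects, report by arm the number and percent of participants with the event at any of the 6 interviews, with a risk difference and an exact confidence interval. List answers to the catch-all question by event type, so that unrelated events are not pooled.

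If severity is also compared, take each participant's worst rating over the interviews, scored 0 = none, 1 = mild, 2 = moderate, 3 = severe, over everyone interviewed, and use a test for two independent arms.

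This needs a few sentences and no new data. The cost is one more column in the safety table and mean severity values lower than those taken over affected participants only.

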4. STUDY DESIGN

4.1 OVERALL DESIGN

The design for this study is a pilot, randomized, double-blind, sham-controlled, clinical trial which will be used to investigate the mechanism of action of 10 Hz tACS in subjects with MDD, as well as determine the relationship between physiological changes and clinical changes. We are recruiting from a clinical population. Participants will be 20 males and non-pregnant females ages 18-70 with unipolar, non-

psychotic MDD, free of benzodiazepine and anticonvulsant medication, who have a HDRS-17 > 8 and are at a low risk for suicide according to the Hamilton Depression Rating Scale as well as the Columbia Suicide Severity Rating Scale (C-SSRS). All women of child-bearing potential will be asked to take a pregnancy test during the initial session to determine eligibility for the study; nursing or pregnant subjects will be excluded from participation, and all women of child-bearing potential will be required to use an appropriate form of birth control throughout their participation. These individuals will be outpatients and may or may not seek mental health care from a family practitioner, therapist, or psychiatrist.

This is a single-site, pilot clinical trial with 2 arms. Due to the Covid pandemic recruitment was slower than expected. We anticipate to complete study enrollment until 12/2022. Subjects will be randomly assigned to one of two arms: active sham stimulation or 10 Hz (alpha) tACS. We will use the XCSITE100 stimulator designed by PulvinarNeuro for investigational purposes to deliver stimulation over five consecutive days. Subjects will stay in a relaxed yet experimentally controlled state by watching a nature movie such as "Reefscape" during stimulation. The initial session (D1) and D5 will take approximately 4 hours. D2-D4 will take 90 minutes. The 2-week follow-up will take approximately 3 hours. We estimate that total participation to be approximately 17 hours.

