6.1.2 DOSING AND ADMINISTRATION

The research team will first measure each subject's head using the 10-20 system to determine the electrode locations. Subjects will then be fitted with the 3 electrodes for stimulation: two 5x5cm electrodes placed over F3 and F4, and one 5x7cm electrode placed over Cz. Electrodes will be carbon rubber, with Ten20 conductive paste applied. During stimulation, the subject will be in a relaxed and experimentally controlled state by watching a nature movie (such as *Reefscapes*). One session of stimulation will be performed per day, for 40-minutes. Before and after each stimulation session, an eyes open and eyes closed resting state EEG will be performed.

The stimulation waveforms used in this study are sham/placebo stimulation and 10 Hz tACS at 1 mA zero-to-peak amplitude. Sham/placebo stimulation includes 20 seconds of ramp-in to 40 seconds of 10 Hz tACS at 1 mA to 20 seconds of ramp-out, for a total of 80 seconds of stimulation. This is intended to mimic the skin sensations (e.g., itching, burning, tingling) that are experienced at the onset of stimulation, assisting with blinding the subject's assignment. 10 Hz tACS also has a ramp-in and ramp-out of 20 seconds, with 40-minutes of stimulation at an amplitude of 1 mA, for a total of 2440 seconds of stimulation.

Stimulation devices will be pre-programmed, and codes will be randomized to one of the two experimental arms. Researchers will enter the subject-specific code into the tablet that controls the XCSITE100 device and will monitor subjects during the 40-minutes of the stimulation. Research personnel will be thoroughly trained and have trainings documented on the transcranial stimulation device and will be present during all stimulation sessions. To monitor side effects of stimulation a stimulation effects questionnaire will be administered after each stimulation session.

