6.3 MEASURES TO MINIMIZE BIAS: RANDOMIZATION AND BLINDING

Randomization

[name], a [name] Lab member, will randomize 20 6-digit codes, which will be used by the study coordinator and research assistants. These codes are directly linked to which treatment subjects receive (sham/placebo or 10 Hz tACS at 1 mA) and will be entered into the XCSITE tablet. The assignment of each subject cannot be determined by looking at the codes (e.g., codes are not sequential, code assignment is not based on "odd" or "even" numbers). [name] has no other responsibility in the study other than providing these randomized codes. If [name] leaves the [name] Lab, another equivalent researcher who does not work with human subjects will perform this task.

Blinding

The study is double-blind. This means that the subject and the researchers are unaware of each subject's assignment until the completion of all data collection. This is accomplished using the randomization codes described above. Furthermore, this study utilizes an active sham stimulation. This means that the sham/placebo condition includes some stimulation, mimicking the skin sensations associated with tACS. Blinding success is tested on D5 with two separate questionnaires for operator and participant. In our

previously concluded trial, subjects in the sham and 10 Hz tACS groups responded similarly to the blinding questionnaire, indicating that our active sham stimulation successfully blinded the subjects.

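### Section 9.4.4 names paired t-tests to compare adverse-event severity between two unpaired parallel arms and does not say how each participant's six interviews are combined (minor, safety analyses only)

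*Combined protocol and SAP*

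**What the plan says.** Section 9.4.4 (Safety Analyses) has the structured interview given after every stimulation session and at follow-up, "for a total of 6 time points per participant". A clinician rates the responses under Section 8.3, where severity is mild, moderate or severe. The between-arm analysis is then: "Paired t-tests will be calculated per adverse effect to determine if there are any differences in adverse effect severity between groups", the groups being sham/placebo and 10 Hz tACS. The only other instruction is to describe severity per adverse effect by mean and standard deviation.

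On the design, Section 4.1 says: "Subjects will be randomly assigned to one of two arms: active sham stimulation or 10 Hz (alpha) tACS". Section 6.1.2 says that "codes will be randomized to one of the two experimental arms", and Section 6.3 that a lab member "will randomize 20 6-digit codes, which will be used by the study coordinator and research assistants". Section 9.2 plans "with a total of 20 subjects (10 in each group").

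Two neighbouring sentences bear on the reading. For the stimulation questionnaire, Section 9.4.4 also names a paired t-test but attaches a random effect for subject. For baseline data, Section 9.4.5 names paired t-tests or chi-square tests without saying what is compared with what.

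**The concern.** A paired t-test analyses differences within natural pairs: the same person twice, or matched persons. Here each participant receives one arm only, and no section describes matching, blocks of two, or crossover. The test named therefore does not fit the comparison named in the same sentence, and nothing elsewhere corrects it. An analyst who followed it person by person would have to choose who is paired with whom, and a pre-specified p-value should not depend on that choice.

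The second gap is separate. Six ratings per participant are collected, but the interview sentence neither reduces them to one value nor includes a subject term, although the questionnaire sentence in the same section has one. How the six ratings enter the test is left to the analyst. At stake is the reliability of the between-arm comparisons of adverse-effect severity.

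**Working it through.** **Inputs from the documents.** 20 participants, 10 per arm (Section 9.2). Interviews: 5 stimulation sessions + 1 follow-up = 6 per participant, which reproduces the stated figure. Significance threshold 0.05 (Section 9.4.1), taken as two-sided because sidedness is not stated. The documents give no effect size, SD, within-person correlation or event rate for adverse-effect severity; every such value below is an assumption.

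**1. Dependence on the pairing (exact arithmetic, illustrative split).** One value per person, mild event = 1, none = 0; 5/10 events on tACS and 1/10 on sham. The mean difference is 0.4 under any pairing.
- The sham event is paired with a tACS event (5 of 10 possible partners): differences are four +1 and six 0. Sum of squares 4 − 10×0.4² = 2.4; SE = √(2.4/9/10) = 0.163; t = 0.4/0.163 = 2.45 on 9 df; p = 0.037.
- It is paired with a non-event (the other 5 of 10): five +1, one −1, four 0. Sum of squares 6 − 1.6 = 4.4; SE = √(4.4/9/10) = 0.221; t = 1.81 on 9 df; p = 0.104.
- Unpaired t-test: variances 2.5/9 = 0.278 and 0.9/9 = 0.100; pooled 0.189; SE = √(0.189×2/10) = 0.194; t = 2.06 on 18 df; p = 0.054.

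With 6/10 versus 1/10, the same steps give a paired p of 0.015 (60% of pairings) or 0.052 (40%). In 40,000 simulated trials per setting with normal data, two random pairings disagreed on p < 0.05 in 4%, 9% and 15% of trials at assumed standardised differences d of 0, 0.5 and 1.0.

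**2. Error rate and power with one value per person, normal data.** Type I error of the arbitrarily paired test is 5.1% by simulation. Degrees of freedom fall from 18 to 9 and the critical t rises from 2.10 to 2.26. Power from the noncentral t, with noncentrality d×√(10/2):

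| Assumed d | Unpaired (18 df) | Arbitrary pairs (9 df) |
|---|---|---|
| 1.0 | 56.2% | 51.4% |
| 1.325 | 80.0% | 75.1% |

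The loss is about 5 points.

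**3. The six interviews.** If all 6×10 = 60 records per arm were treated as independent, the variance of the arm difference would be understated by a factor of 1 + (6 − 1)×ICC, where ICC is the intraclass correlation. Simulated type I error, normal data:

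| Assumed ICC | Factor | 60 arbitrary pairs | Unpaired 60 vs 60 | Unpaired, one mean per person |
|---|---|---|---|---|
| 0.2 | 2.0 | 16.4% | 16.6% | 5.1% |
| 0.35 | 2.75 | 24.2% | 24.5% | 5.0% |
| 0.5 | 3.5 | 30.3% | 30.2% | 5.0% |

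Paired and unpaired columns agree, so this inflation comes from ignoring the participant, not from pairing. With sparse four-category ratings (assumed 85/10/4/1% none/mild/moderate/severe) it is 11%, 16% and 22% at the same latent correlations.

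**4. Pairing by time point.** The two arm means at each interview could be paired, giving 6 pairs. This is not arbitrary, but it ignores the participant too: simulated type I error is 5.0%, 10.0%, 23.0% and 37.5% at assumed ICC 0, 0.1, 0.3 and 0.5.

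**The case against.** The strongest reply is that this is a slip of wording: an independent-samples test was meant, and the subject term was dropped from the second of two parallel sentences. The questionnaire sentence has that term, and the primary analysis in Section 9.4.2 uses repeated-measures ANOVA or a mixed model. That is probably right and keeps the matter small. It does not remove it, because the text nowhere corrects the test, the word recurs in two other sentences, and reading it as independent still leaves six ratings per person unassigned.

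It is also fair that arbitrary pairing costs little. Type I error holds near 5%, and for none/mild data the loss can vanish: at assumed event rates of 50% versus 10%, power is 48.9% randomly paired and 47.1% unpaired. What remains is that the p-value turns on an arbitrary choice.

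A reader might infer three stronger things that the documents do not support:
- That pairing inflates false positives. It does not, with one value per person.
- That the plan pools 60 records per arm and so has a 16% to 30% error rate. The plan does not say so; those figures describe one reading that it leaves open, under assumed correlations.
- That the analysis cannot be run at all. Pairing arm means by time point can be run, although it handles repeated ratings badly.

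**Conclusion.** Wrong as written, minor in consequence. A paired t-test does not fit a comparison of two parallel arms without matching, and the handling of six interviews per participant is unspecified. Pairing people makes the p-value depend on the pairing (0.037 or 0.104 in the 5/10 versus 1/10 illustration) and, with normal data, costs about 5 points of power. Inflation to about 16% to 30% is conditional on pooling the records and on assumed ICC values of 0.2 to 0.5.

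The scope is secondary safety comparisons. A reader might infer that the trial's main results or participant safety are compromised. They are not: the primary EEG, HDRS17 and chi-square analyses do not use this test, and decisions on individual participants rest on clinician review (Sections 8.2.3 and 10.1.6), not on these p-values.

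**What to change.** In the interview sentence of Section 9.4.4, replace the paired t-tests with one of:
- an independent-samples comparison between arms of one pre-stated value per participant per adverse effect, for example the mean or the worst severity over completed interviews; or
- a mixed model with arm, time point and a random subject effect.

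State how the severity ratings and the absence of an effect are coded, and report counts per severity category by arm. Section 9.4.1 already provides that "categorical data will be described using counts/percentages".

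Two related corrections: rename the questionnaire analysis as a mixed model, which is what a random effect for subject implies; and delete the word paired in Section 9.4.5 if the arms are what is compared.

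The cost is wording only, with no new data. A worst-severity summary discards timing and repeat episodes, and a mixed model on a four-level scale with 10 per arm is approximate.

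An exact rank-sum test on the participant-level value is an option, not a requirement. If it is chosen, its cost should be stated. For none/mild data it is conservative and loses about 18 to 19 points of power against the unpaired t-test in these assumed scenarios: 29.5% against 47.1% at event rates of 50% versus 10%, 47.4% against 65.9% at 60% versus 10%, and 23.8% against 42.6% at 40% versus 5%.
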